DSM-5 Self-Rated Level 1 Cross-Cutting Symptom Measure (DSM-5 CCSM): The DSM-5 CCSM is a 13-item self-report questionnaire that assesses mental health domains that are important across psychiatric diagnoses.

Distress Intolerance Index (DII): The DII is a 10-item self-report questionnaire about how individuals handle difficult situations and emotions.

Hamburg Hannover Agitation Scale (H2A): The HHAS is an 11 item self-report questionnaire used to measure symptoms of agitation over a one-week period.

Self-Injurious Thoughts and Behaviors Interview (SITBI): The SITBI assesses the presence, frequency, and characteristics of a wide range of self-injurious thoughts and behaviors, including suicidal ideation, suicide plans, suicide gestures, suicide attempts, and nonsuicidal self-injury

Brief Approach Avoidance Coping Questionnaire (BACQ): The BACQ is a 12-item self-report questionnaire that measures approach and avoidance styles of coping with difficult situations and problems. Items are scored on a 5-point scale.

Barratt Impulsiveness Scale SR (BIS): The BIS is a 30 item self-report questionnaire that measures impulsivity and behavioral control in the domains of motor control, non-planning, and attention.

Conflict Tactics Scale (CTS2): The CTS2 short form is a 20-item questionnaire that assesses conflicts used during partner disagreements. 10 questions are about the partner doing to the subject and 10 questions are the subject doing to the partner.

Protective Factors (deterrents) of Suicide

General Belongingness Scale (GBS): The GBS is a 12-item measure to assess a sense of general belongingness.

MMB Treatment Protocol

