In UPWARD, UPWARD Extension and UPWARD-S, if suicidality is endorsed with a score of greater than 1 on EPDS item #10 or PHQ-9 item #9 or on any of the self-report questionnaires (such as the SITBI or CCM), subjects will be prompted to complete the CS-S to assess risk of suicidality. Study subjects will also be given the national suicide [contact]) and informed that answers to online questionnaires are not monitored in real time. A positive score on questions 3, 4, or 5 on the CS-S, indicating intention or plan for suicidality, will prompt a safety call by study physicians. Suicidality expressed during the course of clinical or qualitative interviews, either through discussion, endorsement of the suicidality item on the MINI mood module, endorsement of items 3, 4, or 5 on the suicidality module of the MINI, or via scoring >2 on the MADRS item 10, will prompt study staff to complete the CS-S with the participant. A positive score on items 3, 4, or 5 of the CS-S administered by staff will also prompt a safety call by study physicians. In addition, subjects will be told by study staff to call their community providers and go to their nearest emergency room. Endorsement of items 3-5 on the CS-S prompting a physician safety call has been the threshold used in previous studies at the collaborating site (University of Colorado Boulder). As this is a community-based study with collaboration from community physicians, these providers dictate treatment. We will notify community providers directly via phone or fax within 24 hours from report of positive scores on CS-S items 3-5.

VI. BIOSTATISTICAL ANALYSIS

Preliminary Analyses: Differences between the MMB and UC in demographic characteristics and depression related characteristics (e.g., symptom severity, comorbidity) will be assessed using Chi-square test for binary variables, Cochran Mantel Haenszel tests for categorical variables, and t-tests for continuous variables. Variables that show significant group differences and predict outcome will be entered in analyses as covariates; AD exposure will be included as a covariate. All participants will be considered evaluable for analysis (intent-to-treat sample). Significance levels will be evaluated at $p < .05$, and effect sizes reported.

Analysis for Specific Aim #1: To test the relative risk for depressive relapse and reduction of symptom burden between women randomized to digital MMB or UC.

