If a participant scores greater than or equal to 15 on the PHQ-9 or greater than or equal to 12 on the EPDS, the online data collection and management system (REDCap) will automatically provide participants with contact information for national mental health crisis resources and for the research study team. Study investigators will be notified immediately via an algorithm programmed into REDCap. In the UPWARD parent trial and UPWARD-S Arms 1a and 2, study staff at MGH will initiate a clinical response by phone call to assess clinical status and suicidality as soon as possible within 24 business hours of report. The score of 15 is suggested as the threshold for moderate depression.³⁹ Additionally, we will monitor specifically responses to the suicide item (#9) on the PHQ-9: 'Thoughts that you would be better off dead or hurting yourself in some way.' and the suicide item (#10) on the EPDS: 'The thought of harming myself has occurred to me' for all study participants. If a participant endorses either of these items with a score of 1 or greater, REDCap will automatically route participants to fill out the Columbia Suicide Severity Rating Scale (CS-S) and provide participants with contact information for national mental health crisis resources and for the research study team. Study investigators and staff will be automatically notified by the REDCap system for a positive score on questions 3-5 of the CS-S in order to provide outreach as soon as possible within 24 hours and assessment of the patient by a study doctor. In UPWARD-S, endorsement of current suicidal ideation on the SITBI or CCM item (#11) will also automatically route participants to fill out the CS-S. Any endorsement of items 1-5 of the CS-S will prompt administration of the full CS-S to capture duration and intensity of suicidal ideation and/or behaviors. Furthermore, any participant who misses a scheduled assessment point will be contacted immediately by study staff. Study staff will continue to try to reach participants until a participant indicates that they no longer wish to be contacted or the participant has reached six months postpartum by their estimated date of delivery, whichever comes first. Throughout the study, all participants also will be encouraged to contact the study staff at the first sign of increased depression.

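### In UPWARD-S Arm 1a, a suicide attempt reported on the SITBI at M3 triggers no stated automatic alert unless CS-S items 3-5 or a depression total is also positive

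*Combined protocol and SAP*

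**What the plan says.** Section VII (Risks and Discomforts) describes two automatic notifications from online self-report.

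- **Symptom totals.** For a PHQ-9 total of 15 or more, or an EPDS total of 12 or more, "Study investigators will be notified immediately via an algorithm programmed into REDCap". In UPWARD-S Arms 1a and 2, staff then telephone within 24 business hours to assess clinical status and suicidality.
- **The Columbia scale (CS-S).** "Study investigators and staff will be automatically notified by the REDCap system for a positive score on questions 3-5 of the CS-S", followed by outreach within 24 hours and assessment by a study doctor. Section V (Prospective Follow-up and Community Outreach) says what these items mean: "A positive score on questions 3, 4, or 5 on the CS-S, indicating intention or plan for suicidality, will prompt a safety call".

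The SITBI, described in Section V under the additional measures for Arms 1a and 2, covers self-injurious thoughts and behaviours, "including suicidal ideation, suicide plans, suicide gestures, suicide attempts, and nonsuicidal self-injury". Two sentences say what a SITBI answer sets in motion. In Section VII, "endorsement of current suicidal ideation on the SITBI or CCM item (#11) will also automatically route participants to fill out the CS-S". Section V is wider: if suicidality is endorsed "on any of the self-report questionnaires (such as the SITBI or CCM), subjects will be prompted to complete the CS-S". Section VII adds that endorsing any of CS-S items 1-5 "will prompt administration of the full CS-S to capture duration and intensity of suicidal ideation and/or behaviors".

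Section III makes a suicide attempt a drop criterion in Arm 1a if a study physician finds local care inadequate. Adequate care includes an outpatient appointment within 10 days of the attempt.

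**The concern.** The alert rule responds to depressive symptom totals and to intention or plan. It does not name an attempt, although the SITBI collects one and REDCap already acts on another answer from the same instrument. Stated intent brings a study doctor within 24 hours, while a reported attempt on its own brings no stated alert.

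This matters most in Arm 1a. Suicidal ideation is an entry requirement there, participants are told that online answers are not watched in real time, and the drop criterion needs a physician who knows that an attempt has occurred. What is at stake is the time until a physician reviews a reported attempt. No outcome or analysis is involved.

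**Working it through.** The plan gives no figure to reproduce. The check sets the alert text against the schedule and then sizes the possible delay.

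**1. Can a SITBI attempt answer reach staff automatically?** Under the Section VII wording, only current ideation on the SITBI leads to the CS-S. Under the Section V wording, an attempt could count as suicidality and lead there too. Either way the next step is the CS-S, and notification still needs items 3-5 to be positive. The CS-S is in any case given at every UPWARD-S time point, M3 included, so the routing adds no new trigger. No notification is attached to the behaviour part of the full CS-S.

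**2. Is a scheduled interview there to catch it?** Table 3 (Arm 1a) against the telephone contacts in Section V (UPWARD-S and Aim 1a):

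| Time point | SITBI | Scheduled interview |
|---|---|---|
| Baseline | yes | MINI, MADRS, CGI; qualitative interview near this point |
| M3 | yes | none |
| Third trimester | yes | MINI mood, MADRS, CGI |
| 3 months postpartum | yes | MINI mood, MADRS, CGI |
| 6 months postpartum | yes | MINI mood, MADRS, CGI |

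M3 is the only one of the four post-baseline SITBI points without an interview.

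**3. How long until the next interview?** The documents do not fix these timings, so I assume M3 is 13 weeks after enrolment, enrolment is at 8, 12 or 16 weeks' gestation, and the third-trimester interview is at 28, 32 or 36 weeks.

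Wait = interview week − (enrolment week + 13)

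| Enrolment | M3 | Interview at 28 | Interview at 32 | Interview at 36 |
|---|---|---|---|---|
| 8 | 21 | 7 | 11 | 15 |
| 12 | 25 | 3 | 7 | 11 |
| 16 | 29 | left out | 3 | 7 |

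The combination of 16 and 28 weeks puts M3 (29) after the interview (28), contrary to the order in Table 3, so it is left out. The rest run from 3 to 15 weeks, with 7 in the middle case (enrolment at 12, interview at 32).

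**4. What else must stay silent?** Arm 1a women complete the CS-S, PHQ-9 and EPDS every two weeks according to Table 3. The Aim 1a text says monthly; I use the two-weekly schedule, which favours the plan.

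- Before M3: 13/2 = 6.5, so about 6 forms. Those that follow the attempt must all be negative on CS-S 3-5 and below both totals.
- At M3: the same three instruments must also raise no alert.
- After M3: 15/2 = 7.5, so at most 7 forms in the longest wait; 7/2 = 3.5, so about 3 in the middle case.

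**The case against.** The strongest reply is that the SITBI is only a back-up. The main screen is the two-weekly CS-S, PHQ-9 and EPDS, and a woman who has made an attempt may well trip one of them before, at or after M3. The CS-S recall period is not stated; if it reaches back to the previous form, few attempts might leave items 3-5 negative. This stands, and it narrows the gap considerably. It does not close it, because none of those triggers is an attempt.

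There are also indirect routes. Section VII says that "any participant who misses a scheduled assessment point will be contacted immediately by study staff". Section IX has continuing review of binders and databases and twice-weekly safety meetings. Section IV has letters to community providers after baseline and again in the third trimester. If staff administer the full CS-S to a woman who endorses only items 1 or 2, they could learn of the attempt then. The text does not say who administers it in that case; the only named user is the study doctor, during the risk assessment. Section VII also engages a suicide-research consultant and justifies the items 3-5 threshold by earlier use. All of this lowers the chance of delay, but none of it is a stated trigger on a reported attempt.

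Three other sentences look like answers but are not clearly so. Section VII says that endorsed suicidality starts a physician protocol, but within a paragraph on telephone contacts. Section IX promises one MINI call per trimester in wording that fits randomized women, and Arm 1a is not randomized. The pooled interview list in Section V includes a post-intervention interview, but Arm 1a has no intervention and Table 3 has no such column.

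Finally, no requirement is breached. The drop criterion governs what follows a known attempt and sets no deadline for detecting one. An attempt first reported at M3 may already be more than 10 days old, since the previous SITBI was at baseline. That is correct, and I do not claim a breach.

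**Conclusion.** The point holds for Arm 1a at M3: 125 women and one SITBI time point. An attempt reported there raises no stated automatic alert if CS-S items 3-5 are negative and both totals are below threshold. Under the assumed timings, the delay to the third-trimester interview could be 3 to 15 weeks (middle case 7), provided that all the interim screens and indirect routes also miss it. The 3 to 15 weeks is a range over assumed calendars and says nothing about probability. The documents do not allow the frequency to be estimated. This is a cheap safety improvement and not a flaw in the trial's inference.

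A reader might infer more, and the documents do not support it:

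- **That Arm 2 has the same gap.** Table 4 cannot be read with certainty in the available text. Its columns appear to place the MMB qualitative interview alongside the post-intervention SITBI. Section V omits a post-intervention interview in one list and includes it in another.
- **That the two-weekly CS-S also lets attempts through.** This would require the online form to carry a behaviour item, which the text does not confirm.
- **That attempts would go unnoticed.** The text shows a missing automatic trigger only. The actual REDCap programming may do more than is written.
- **That the parent trial and the Extension are affected.** Neither schedules the SITBI.

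**What to change.** In Section V (Prospective Follow-up and Community Outreach) and Section VII, add a suicide attempt since the last assessment, endorsed on the SITBI, to the answers that automatically notify investigators. Apply it wherever the SITBI is self-completed, so that Arm 2 can share the rule. Leave the CS-S items 3-5 threshold as it is. It would also help to state who administers the full CS-S when only items 1 or 2 are endorsed. The clinical response to the alert is for the sponsor to decide.

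The cost is one more REDCap condition on an answer already collected, a sentence in each of the two sections, and a few more alerts to review. Limiting it to the period since the last assessment avoids repeat alerts for past attempts. If the alert is already programmed, only the text needs to change.

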Preventing Depressive Relapse in Pregnant Women With Recurrent Depression

NCT03623620

5/17/2021

PARTNERS HUMAN RESEARCH COMMITTEE DETAILED PROTOCOL

I. BACKGROUND AND SIGNIFICANCE

UPWARD Study

Historically, pregnancy has been viewed as a protective time with respect to risk for psychiatric illnesses. This assumption, along with ethical concerns regarding the conduct of randomized trials during pregnancy, has resulted in limited evidence regarding how to best manage depression during pregnancy. In contrast, robust evidence indicates that depression is prevalent during pregnancy and is associated with increased risk of adverse correlates and consequences for offspring, including obstetrical and neonatal outcomes such as shorter gestational age, increased rates of preterm delivery and lower birthweight; affective and behavioral dysregulation during childhood; and increased risk for later psychopathology¹⁻³. The most robust predictor of depression during pregnancy is history of depression, and women with recurrent depression experience high rates of relapse depression during pregnancy^{4,5}, underscoring the pragmatic and ethical need for definitive evidence regarding how to mitigate risk of depressive relapse during this important developmental transition.

The current treatment guideline and standard of care for preventing depressive relapse among adults with a history of recurrent major depressive disorder (MDD) is maintenance antidepressants (AD), which poses unique challenges for the management of depression for pregnant women with recurrent depression⁶⁻⁹. Decisions regarding maintenance relative to discontinuation of AD during pregnancy require a weighing of increased risk of relapse associated with AD discontinuation, on one hand, versus the known and unknown risks of fetal exposure to AD on the other. Rates of subsequent relapse are significantly higher among women with recurrent depression who discontinue AD than among those who maintain, and depression during pregnancy is one of the greatest risk factors for postpartum depression^{10,11}. Postpartum depression not only places the mother at risk for refractory illness, but also can have long-term negative consequences on child development and behavior^{12,13}.

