all participants (at baseline, post-intervention, third trimester, 3 months postpartum, and 6 months postpartum). Participants will be offered the option to schedule phone interviews online via Calendly. Those who do not wish to use the online scheduling platform can choose to schedule directly with the study team via email, phone call, or text message on an encrypted study cell phone. Changes in medication and usage and dosage, as well as any relapse in depressive symptoms since the last phone contact, will be gauged during each phone call by study staff. Please see **Table 1** below for listing of assessments administered at each time point.

[figure not shown]

Table 1. UPWARD Measurement Schedule

UPWARD Study	Baseline	M1	W6	M2	Post-Intervention	M3	M4	M5	3T	M6	M7	M8	3PP	M10	M11	M12	6PP	12P P***
MINI full	X																	
MINI mood	X				X					X				X				X
MADRS	X				X					X				X				X
EPDS	X	X	X	X		X	X	X	X	X	X	X	X	X	X	X	X	
PHQ-8																		X
PHQ-9*	X	X	X	X		X	X	X	X	X	X	X	X	X	X	X	X	
CS-S**	X																	
CGI	X				X					X				X				X
PGI	X	X	X	X		X	X	X	X	X	X	X	X	X	X	X	X	
GAD-7	X	X	X	X		X	X	X	X	X	X	X	X	X	X	X	X	
PSS-10	X					X		X					X				X	X

WHODAS 2.0	x				x			x			x			x	
CSQ-8 (UC)	x				x									x	
CSQ-8 (MMB)					x										
CTQ	x														
PROMIS	x														
FFMQ	x		x		x									x	
RRS	x		x		x									x	
SCS	x		x		x									x	
SSQ-SF	x				x						x			x	
RSQ-MEP	x														
LEL	x													x	
LEIDS-R	x		x		x										
EQ	x		x		x									x	
CSI	x													x	
AToM	x				x			x			x			x	
PSA	x		x		x			x							
PSQI	x				x						x			x	
Positive Mood Diary	x		x		x										x
DPES Joy Subscale	x		x		x						x			x	x
CERTS Unresolution Subscale	x														
CERQ Acceptance Subscale	x														
NEO-FFI Neuroticism Domain	x														
SRET	x		x		x						x			x	x
ASQ-3											x			x	x
ASQ-SE-2											x			x	x
IBQ											x			x	x
IMP											x			x	

PSI-4-SF																x
BITSEA																x
PRFQ																x
KPCS																x
BAM-13																x
My Baby's Day																x
PAT																x
CASP																x
PANAS (post CASP; present moment instruction)																x
ECBQ																x

*PHQ-9 will also be administered every two weeks

** the CS-S will be conditionally delivered at any time point after PHQ-9 Q9 >0 or EPDS Q10 >0

*** only administered to participants that opt-in to do the additional 12-month assessment (UPWARD-Baby)

UPWARD Extension

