The final 100 participants in the UPWARD sample of 600 individuals will participate in an abbreviated version of the UPWARD procedures. These 100 women will be recruited via the same platform of BabyCenter, screened and enrolled based on the same entry criteria, and similarly randomized to the MMB intervention or Usual Care. However, the only differences will be that these final participants in this group of 100 who are randomized to the treatment group will not receive the coaching that is typically involved in the MMB intervention. This will further investigate our research aims to assess the extent to which this modified version of MMB is still an effective means of preventing depressive relapse in a perinatal population. Moreover, these final 100 participants will not receive any follow-up clinical interviews or relapse determination calls after the initial screening and baseline calls. Participants will be randomized after the baseline call, either through a phone conversation or via email. They will instead be prospectively followed through 3 months postpartum via the same battery and schedule of self-report questionnaires given to the other UPWARD participants through this timepoint. If any participant endorses items 3, 4, or 5 on the C-SSRS via these self-report questionnaires, the same suicidality safety protocol will be triggered as outlined below. The information about the delivery and newborn outcomes that would typically be collected during the 3 months postpartum interview will now be administered as a self-report survey with the rest of the questionnaires for this timepoint.

Table 2. UPWARD Extension Measurement Schedule

UPWARD Study	Baseline	M1	W6	M2	Post-Intervention	M3	M4	M5	3T	M6	M7	M8	3PP
MINI full	x												
MINI mood	x				x				x				x
MADRS	x				x				x				x
EPDS	x	x	x	x		x	x	x	x	x	x	x	x
PHQ-9*	x	x	x	x		x	x	x	x	x	x	x	x
CS-S**	x												
CGI	x				x				x				x
PGI	x	x	x	x		x	x	x	x	x	x	x	x
GAD-7	x	x	x	x		x	x	x	x	x	x	x	x
PSS-10	x					x			x				x
WHODAS 2.0	x					x			x				x
CSQ-8 (UC)	x					x							
CSQ-8 (MMB)						x							
CTQ	x												
PROMIS	x												
FFMQ	x		x			x							
RRS	x		x			x							
SCS	x		x			x							
SSQ-SF	x					x							x
RSQ-MEP	x												
LEL	x												
LEIDS-R	x		x			x							
EQ	x		x			x							
CSI	x												
AToM	x					x			x				x
PSA	x		x			x			x				
PSQI	x					x							x
Positive Mood Diary	x		x			x							

DPES Joy Subscale	x		x		x					x
CERTS Unresolution Subscale	x									

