MGH physicians with perinatal psychiatry expertise will be available via a consult line for community providers of participants enrolled in the UPWARD Study and UPWARD-S. Throughout the study, they will answer questions regarding psychiatric medications and possible treatment options for individual patients determined by their community provider.

MGH study staff trained in interviewing techniques will administer the baseline, qualitative, post-intervention, third trimester, 3 months postpartum, and 6 months postpartum interviews completed for enrollees in UPWARD and UPWARD-S. Those enrolled in UPWARD Extension will complete only the screening and baseline calls. Participants will then be randomized either over the phone or via email. Baseline clinical instrument results will be reviewed and confirmed by study principal investigators to ensure eligibility. We will send a birth acknowledgement by regular mail, email, or both after delivery, and at periodic times during the study, we will send reminders of study engagement or gifts of nominal value to increase cohort retention.

In the UPWARD Study, in addition to regularly scheduled self-report questionnaires and phone contacts, relapse determination calls will be made to any participant scoring ≥ 15 on the monthly PHQ-9 or ≥ 12 on the EPDS. This relapse determination call will consist of study staff asking about the date of relapse and administering the MINI mood module and MADRS retrospectively to assess depressive symptoms during the time of relapse. If a depressive relapse has already been confirmed via clinical interview with the MINI mood module or the MADRS within a week of completion of self-report answers to either the PHQ-9 or EPDS, no relapse determination call will be made. However, if a depressive relapse is not documented during the clinical interview with the MINI mood module, but follow-up self-report surveys indicate increased depressive symptoms, a relapse determination call will be made.

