For the analysis of rates of relapse, we will examine time to relapse as rated by the MINI during pregnancy and across the 6-month postpartum follow up using survival analysis. Survival rates will be compared using Cox proportional hazard regression and illustrated in Kaplan-Meier curves (Collett, 1994). However, time to attrition is a competing risk that can be related to time to relapse. We will adopt the subdistribution hazard model (SHM) developed by Fine and Gray to account for the possible non-independence of the censoring mechanism.²⁵

For the continuous outcomes, we will use Hierarchical Linear Models (HLM) as our primary analytic model, which will compare change over time between groups on depressive symptom burden using the PHQ-9. HLM is flexible with respect to the nature of change over time (i.e., linear, piecewise linear, loglinear, etc.), and will accommodate the within subject correlation through the inclusion of random effects at the patient-level, accounting for the patient-to-patient deviations. Pattern-mixture models²⁶ will be used to assess whether important estimates (i.e., intervention effects) are dependent on missing data and to provide overall estimates of effects by averaging over the various missing-data patterns.

Analysis for Specific Aim #2: To explore the specific benefit of MMB relative to AD discontinuation and questions regarding personalization that are of strong interest to pregnant women and their healthcare providers.

H2a: Comparison of MMB to UC among women who discontinue AD: Our analysis will be the same as H1 with both the time-to relapse and continuous outcome models. We predict that rates of relapse and symptom burden among women randomized to MMB who discontinue AD will be significantly superior to those randomized to UC who discontinue AD.

H2b: Treatment Selection Algorithm: We predict that the use of a treatment selection algorithm will differentiate two profiles of women based on pre-treatment characteristics (those who are optimally suited to discontinue AD and engage MMB to minimize their risk of relapse, and those who should continue AD to minimize risk of relapse) and that women who are randomized to the algorithm indicated approach will have significantly lower risk of relapse and symptom burden than women who are randomized to their algorithm contraindicated approach.

Analysis for Specific Aim #3: To test the extent to which digital MMB engages putative targets.

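### Attempts to reach a woman who missed an assessment end six months after her estimated delivery date, leaving little or no time to recover a missed 6-month MINI interview, which has no stated anchor date or window

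*Combined protocol and SAP*

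**What the plan says.** Section VII (Risks and Discomforts) contains the rule for missed assessments. It says that "any participant who misses a scheduled assessment point will be contacted immediately by study staff". Attempts then continue until she no longer wishes to be contacted "or the participant has reached six months postpartum by their estimated date of delivery, whichever comes first".

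Section V (Study Procedures, UPWARD) schedules five telephone contacts for "all participants (at baseline, post-intervention, third trimester, 3 months postpartum, and 6 months postpartum"). At each one, medication changes "as well as any relapse in depressive symptoms since the last phone contact, will be gauged during each phone call".

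Section VI (analysis for Specific Aim #1) defines the relapse analysis: "we will examine time to relapse as rated by the MINI during pregnancy and across the 6-month postpartum follow up using survival analysis".

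Section V (Prospective Follow-up and Community Outreach) gives a second route to a MINI rating: "relapse determination calls will be made to any participant scoring ≥ 15 on the monthly PHQ-9 or ≥ 12 on the EPDS".

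The UPWARD Extension is different: "these final 100 participants will not receive any follow-up clinical interviews or relapse determination calls" after the screening and baseline calls, and its follow-up ends at 3 months postpartum.

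No section gives the 6-month interview a window, names the delivery date it is counted from, or extends contact attempts for it. The 12-month UPWARD-Baby survey, by contrast, is explicitly open until 15 months postpartum.

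**The concern.** The rule promises immediate contact and repeated attempts after a missed assessment, but its end date falls at nominally the same time as the last assessment. For earlier visits there are weeks or months in which to recover a missed interview. For the last one there may be none.

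That interview matters because each call looks back to the previous contact. The 6-month call is the scheduled rating of roughly months 3 to 6 postpartum. If it is missed, a relapse in that period is rated only if the woman completed a self-report form, scored above a threshold and answered the resulting call. A woman who has stopped answering interviews may also have stopped completing forms. The planned Fine and Gray model for relapse and pattern-mixture models for the PHQ-9 address attrition analytically. They do not replace an interview that a later call might have obtained.

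**Working it through.** The documents state no figure for this point, so there is nothing to reproduce first. The check is date arithmetic.

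**Inputs from the documents**
- Stop date S = estimated delivery date (EDD) + 6 months (Section VII).
- Final interview due date F = 6 months postpartum (Section V), anchor not stated.
- Women affected: 600 - 100 Extension women = 500 at most.

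**Chase time = S - F**

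*Interview dated from the EDD:* (EDD + 6 months) - (EDD + 6 months) = 0 days for every woman, whatever the date of delivery.

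*Interview dated from actual delivery:* (EDD + 6 months) - (delivery + 6 months) = EDD - delivery = (40 - gestational week at delivery) x 7 days, taking the EDD as 40 weeks.

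| Week of delivery | Chase time (days) |
|---|---|
| 34 | 42 |
| 36 | 28 |
| 37 | 21 |
| 38 | 14 |
| 39 | 7 |
| 40 | 0 |
| 41 | -7 |
| 42 | -14 |

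A negative value means that attempts end before the interview falls due.

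**Share of women with no chase time (actual-delivery dating)**

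The documents give no distribution of gestational age, so this part is assumption. I took a normal distribution with mean 38.5 to 39.5 weeks and SD 1.6 to 2.0, truncated to 24-42.5 weeks. The share is P(delivery at 40 weeks or later).
- Mean 38.5, SD 1.6: z = (40 - 38.5)/1.6 = 0.94, upper tail 17.4%; 16.9% after truncation.
- Mean 39.5, SD 2.0: z = (40 - 39.5)/2.0 = 0.25, upper tail 40.1%; 35.8% after truncation.
- Whole grid: about 17% to 36%. Without truncation, the upper end is about 40%.
- Share with less than 14 days, including those with none: 59% to 82%.

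**Number of interviews lost**

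This needs a miss rate and a recovery rate, and the documents give neither. Suppose repeated attempts recover half of the missed interviews every h weeks, so that c weeks of chase recover 1 - 2^(-c/h). Over the same gestation grid, the present rule recovers 14-24% of missed final interviews if h = 4, and 47-68% if h = 0.5. An 8-week window recovers 1 - 2^(-8/4) = 75% in the first case and virtually all in the second. The direction is stable, but the count is not determined.

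**The case against.** The strongest reply is that the sentence sits among the suicidality and safety procedures and limits repeated attempts on women who are not responding. It does not say that the interview closes on that date, or that a woman who answers and rebooks is refused. For a woman out of contact, actual delivery may be unknown, so the estimated date is a sensible anchor, and a limit on contact after about 12 months of participation is a defensible choice about burden. This stands as an explanation of the estimated date. But no other rule governs recovery of missed assessments, and staff who follow this one would stop at or near the due date of the last interview.

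Second, the consequence is limited. A woman who has already relapsed loses nothing on time to relapse. Between 3 and 6 months postpartum there are monthly self-reports and two-weekly PHQ-9 forms, and threshold scores on the monthly PHQ-9 or the EPDS trigger a retrospective MINI with a relapse date. This stands as a partial offset.

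Three stronger readings are tempting, and the documents do not support them.
- *A reader might infer that attempts always stop on or before the interview's due date.* Under actual-delivery dating, that is true only for delivery on or after the due date. Women who deliver earlier have some chase time.
- *A reader might infer biased ascertainment,* because the Background links depression in pregnancy to "shorter gestational age, increased rates of preterm delivery and lower birthweight". Dependence on delivery timing arises only under actual-delivery dating. Women who relapsed in pregnancy already have their event. The rule is the same in both arms, so a between-arm bias would need delivery timing or missingness to differ by arm, which is possible but not shown.
- *A reader might put a number on the lost interviews.* With a 20% miss rate and h = 4, 500 women give 100 x (0.75 - 0.24) to 100 x (0.75 - 0.14), or about 51-61. Applying the plan's 30% attrition first (350 women, so 70 missed) gives about 36-43, before women who have already relapsed are removed. Every factor except the 500 and the 30% is assumed.

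**Conclusion.** The concern holds in a limited form and is worth acting on. The cut-off for contact attempts coincides nominally with the last MINI interview, and that interview has neither an anchor nor a window. On either reading the time to recover a missed final interview is poor: zero for all women, or only the days delivered early. The arithmetic rests on the documents alone. The 17-36% with no chase time rests on the assumed gestation distributions and on actual-delivery dating.

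What is at stake is avoidable missing relapse data for about months 3 to 6 postpartum, among those of the roughly 500 parent-trial women who have not already relapsed. The Extension women have no 6-month interview and are not affected. The size of the loss cannot be stated from the documents.

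**What to change.** In the Section VII rule, continue attempts until the woman declines contact or until the later of (a) the current cut-off and (b) a fixed window, for example 8 weeks, after the due date of the 6-month interview. Date that interview from actual delivery where known and from the estimated date otherwise, and say so in Section V.

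Leave the current cut-off unchanged for the Extension women. Their last assessment is at 3 months postpartum, so a window of 3 months plus 8 weeks would generally end before the six months they now have, and would shorten contact set out in a safety paragraph.

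In the Aim 1 relapse analysis, count only relapses with onset up to 6 months postpartum, so that a late interview does not lengthen follow-up.

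The cost is a few sentences, a few more weeks of contact attempts for women who missed the last interview, and slightly longer recall when it is held late.
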